5.1.1.2 Prophylaxis initiation cohort for evaluation

[figure not shown]
Patients will be eligible to enter the cohort on initiation of Takhzyro, Haegarda, or Cinryze as a prophylactic treatment during October 10, 2008 through October 3rd, 2019 (Figure 1). October 2008 was selected as the start of the study period based on the approval date for Cinryze, the earliest of the medications to be approved. Clinical experts confirmed that 2008 reflects the current treatment paradigm of medications targeting the BK pathway and that all new treatments after 2008 reflect a continual shift away from inferior anabolic androgen therapies. The study period was also selected to maximize sample size for this rare disease.

New use will be defined as no use of Takhzyro or Haegarda, during the 180 days prior (washout period), and no use of Cinryze as a prophylactic treatment during this 180-day washout period. Because Cinryze is used for both acute attacks (off label) and prophylaxis, patients will be excluded based on evidence of prophylactic use of Cinryze (see definition in Annex 2) during the 180 days prior to cohort entry and will be required to have continuous enrollment and evidence of recurring use during the 90 days following cohort entry. Patients receiving other prophylactic treatments (see Annex 1) during the baseline period will also be excluded. Each patient will be included only once, on the first qualifying event. Patients will be required to have at least 180 days of enrollment prior to cohort entry to obtain baseline attack rates.

Using this cohort, we will evaluate baseline outcomes. Patients' demographic characteristics will be assessed at cohort entry. Patients' attack rates, and attack-related medical service utilization and costs will be evaluated.

Note: HAE does not have specific ICD9/10 diagnostic codes. We used initiation of HAE specific treatment to identify patients of interest (i.e., patients with HAE). The method of using HAE treatments to identify HAE patients has been used widely in the literature (Tachdjian 2020, Banerji 2020, [Vande Walle 2018](#)).¹⁻³ In addition, there is no indication that HAE treatments are used off-label for non-HAE patients.

Figure 1: Prophylaxis initiation cohort study design diagram

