5.2.1.4 HAE attack rates

Observational studies that evaluate attack rates in claims or EHR data sets are limited. There is currently no validated method to evaluate HAE attacks in claims data.

In creating our definitions of severe and non-severe attacks, we took guidance from clinical experts, treatment guidelines, and published literature that identified symptoms ([Longhurst & Bork 2019](#))⁵ or used diagnoses codes indicative of an attack (Tachdjian 2020).¹ Symptoms and diagnoses codes were cross referenced in a de novo code search to capture both ICD-9 and ICD-10 codes.

Attacks are defined by severity:

- **Severe attack:** Treatment guidelines and empirical data suggest that severe attacks are typically treated in the ED.⁶ For this analysis, severe attack will be defined in two ways: broadly as all-cause ED visits with or without hospitalization and more specifically as HAE ED visits with or without hospitalization. HAE specific severe attacks will be defined by a claim for an ED visit with or without hospitalization that includes diagnoses and drugs indicative of an attack (see Annex 2).
- **Non-severe attack-** Non-severe attacks are treated with on-demand therapy either by self-administration or administration by a healthcare professional. An attack treated by a healthcare professional will be defined as a medical service claim for an on-demand therapy occurring outside an inpatient or ED setting (e.g., physician office). For self-administration, we will estimate the number of attacks treated by calculating the number of doses dispensed based on dispensed quantity and approved dosages. Based on [treatment guidelines](#),⁶ patients should readily have on-demand therapy to treat two attacks, thus we will consider any doses dispensed over the two on-hand dosages of on-demand therapy as evidence of an attack.

Data on the duration of attacks by severity is limited, however attacks generally last between two and five days.⁷ Thus, on-demand therapy administrations by a healthcare professional, ED visits, and inpatient hospitalizations occurring within five days of each other will be considered part of a single attack. In cases where an on-demand therapy administration occurs within five days of an ED visit or hospitalization, the attack will be counted as a severe attack.

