Annex 1: HAE drugs

Generic	Brand (Administration)	Acute Attack Dose	Long-Term Prophylaxis Dose	How Supplied
C1 Inhibitor, Human (plasma derived C1 inhibitor [pdC1INH])	Cinryze* (IV)	Adults† 1,000 units once. Additional 1,000 units IV if no improvement 60 minutes after first dose. (not studied in children)	Adults & Children ≥12 years 1,000 units every 3-4 days Max Dose: 2,500 units or 100 units/kg every 3 days Children (6-11 years) 500 units every 3-4 days Max Dose: 1,000 units every 3 days Short-Term Prophylaxis† (before a procedure) 20 units/kg or 1,000 units immediately prior to procedure	Cinryze 500 units Powder Vial Reconstitute with 5mL SWFI Concentration: 100 units/mL
	Haegarda* (SC)		Adults & Children ≥6 years 60 IU/kg twice weekly (every 3-4 days)	Haegarda 2000 IU Powder Vial Reconstitute with 4mL SWFI Concentration: 500 IU/mL Haegarda 3000 IU Powder Vial Reconstitute with 6mL SWFI Concentration: 500 IU/mL
	Berinert* (IV)	Adults & Children ≥6 year 20 IU/kg once		Berinert 500 IU Power Vial Reconstitute with 10mL SWFI Concentration: 50 IU/mL

Generic	Brand (Administration)	Acute Attack Dose	Long-Term Prophylaxis Dose	How Supplied
Lanadelumab	Takhzyro* (SC)		Adults & Children ≥12 years 300mg every 2 weeks. After 6 months, reduce to every 4-week dosing if patient well-controlled.	Takhzyro 300mg/2mL Solution Vial Concentration: 150mg/mL
C1 Esterase Inhibitor, Recombinant (recombinant human C1 inhibitor [rhC1INH])	Ruconest* (IV)	Adults & Children ≥13 years (non-laryngeal attacks) 50 IU/kg/dose Max Dose: 4,200 IU/dose; 8400 IU per 24 hours	Adults & Children ≥13 years† 50 IU/kg/dose once or twice weekly Max Dose: 4,200 IU/dose once or twice weekly Short-Term Prophylaxis† (before a procedure) 50 IU/kg or 1,000 units immediately prior to procedure	Ruconest 2100 IU Powder Vial Reconstitute with 14mL SWFI Concentration: 150 IU/mL
Ecallantide	Kalbitor* (SC)	Adults & Children ≥12 years 30mg once (administered as three injections of 10mg) Max Dose: 60mg in 24 hours		Kalbitor 10mg/mL Vial Solution for Injection (3 vials per package)
Icatibant	Firazyr (SC)	Adults 30mg once. Repeat administrations in 6-hour intervals. Max Dose: 90mg in 24 hours (EU Pediatric Dosing Weight Based)		Firazyr 30mg/3mL Solution Vial Icatibant 30mg/3mL Solution Prefilled Syringe
Berotrastat	Orladeyo* (Oral)		Adults & Children ≥12 years 150 mg once daily. Adjustment: 110mg once daily for hepatic impairment or GI reactions.	Orladeyo 110mg Capsule Orladeyo 150mg Capsule

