Generic	Brand (Administration)	Acute Attack Dose	Long-Term Prophylaxis Dose	How Supplied
Danazol	Danocrine (Oral)		
Adults 200 mg twice or three times daily. 100mg every other day also possible. If favorable response after 1-3 months, reduce dose by half. Max Dose: 600mg/day
 
Children >16 years Initially 2.5mg/kg/day (max initial dose: 50mg/day) for ~2 weeks. Then triturate to max tolerated dose and reduce interval to every other day or every third day. Max Maintenance Dose: 5mg/kg/day or 200mg/day
 
Short-Term Prophylaxis† (before a procedure) 2.5 to 10mg/kg/day. Administer 5 days before and 2-3 days after procedure.
	Danazol 50mg, 100mg, 200mg Capsule Danocrine 50mg, 100mg, 200mg Capsule
Tranexamic Acid	Cyklokapron Lysteda (Oral)		
Adults† 1g twice daily. Adjust dose as needed to between 0.25g and 1.5g twice daily. Max Dose: 3.9g/day
 
Pediatrics† 20mg/kg twice daily. Adjust dose as needed to between 10mg/kg twice daily and 25mg/kg three times daily.
	Lysteda 650mg Tablet Tranexamic Acid 650mg Tablet

Generic	Brand (Administration)	Acute Attack Dose	Long-Term Prophylaxis Dose	How Supplied
Aminocaproic Acid	Amicar (Oral)		
Adults† First Month: 16g per day, in divided doses every 4-6 hours. Maintenance Dose: 2g three times daily. Adjust dose as needed to between 1g twice daily and 4g three times daily. Max Dose: 36g/day
 
Pediatrics† 0.05g/kg twice daily. Adjust dose as needed to between 0.025g/kg twice daily and 0.1g/kg twice daily.
	
Amicar 0.25g/mL Oral Solution (236.5 ml bottle) Amicar 500mg, 1000mg Tablet Aminocaproic Acid 0.25g/mL Oral Solution (236.5 ml bottle) Aminocaproic Acid 500mg, 1000mg Tablet

Oxandrolone	Oxandrin (Oral)		
Adults† 10mg daily. Adjust dose as needed to between 2.5mg every three days and 20 mg daily.
 
Pediatrics† 0.1mg/kg daily. Adjust dose as needed to between 2.5mg weekly and 7.5mg daily.
	
Oxandrolone 2.5mg Tablet Oxandrolone 10mg Tablet

Methyltestosterone	Android Methitest Testred Virilon (Oral)		
Adult Men† 10mg once daily. Adjust dose as needed to between 5mg every three days and 30mg daily.
 
Not recommended in women and children
	
Android 10mg Capsule Methyltestosterone 10mg Capsule Testred 10mg Capsule Methitest 10mg Tablet

Generic	Brand (Administration)	Acute Attack Dose	Long-Term Prophylaxis Dose	How Supplied

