Stanozolol	Winstrol (Oral)		Adults† 2mg daily. Adjust dose as needed to between 1mg daily and 6mg daily. Pediatrics† 0.5mg daily. Adjust dose as needed to between 0.5mg weekly and 2mg daily.	?

IU = International Units; IV = Intravenous Administration; SC = Subcutaneous Administration; SWFI = Sterile Water for Injection

† = Off-Label Indication; * = Brand-Name Only (Brand Exclusivity); ? = No results in pharmacy databases

Drugs Indicated Only for HAE: Cinryze, Haegarda, Berinert, Takhzyro, Ruconest, Kalbitor, Firazyr, Orladeyo

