Android Methitest Testred Virilon (Methyltestosterone)	NDCs: 00187-0902-01 00115-1408-01 00187-0901-01 00115-7037-01	Clinical Pharmacology Database²⁰
Winstrol (Stanozolol)	NDCs: 0024-2253-04??	Clinical Pharmacology Database²⁰
Prophylactic use of Cinryze and Ruconest	Algorithm and code lists	Source
Cinryze prophylactic use	Cinryze is indicated for prophylaxis, but is used off-label for acute attacks. Prophylactic use will be defined as continuous refills of Cinryze averaging ≥ 1500 IU/week for ≥ 90 days.	Riedl 2018²²
Ruconest prophylactic use	Ruconest is indicated for on-demand use, but is used off-label for prophylaxis. Patients with Ruconest prophylactic use will be excluded from the cohort. Prophylaxis use will be defined as continuous refills of Ruconest averaging 50 IU/kg once weekly for 90 days.	Riedl 2018²²
every four-week	Used to determine if a dose reduction occurred.	

administration of Takhzyro	This will be measured over a 90-day follow-up period based on total dose <= 1200 mg over that period. The 1200 mg is based on three 300 mg injections plus one additional injection to account for potential variation in exact timing.	
Attack severity	Algorithm and code lists	Source
Severe	
ED visit with/without hospitalization, identified based on “Type of service” coded as inpatient or emergency room. Events identified as HAE-specific include at least one of the following diagnose (as a primary diagnosis for hospitalizations /or treatments indicative of an attack:
 
 € Codes often associated with HAE: ICD-9-CM 277.6 or ICD-10-CM D84.1 € Angioedema diagnosis: ICD-9-CM 995.1 or ICD-10-CM T78.3* € Administration of on-demand HAE treatment € Diagnosis of swelling, abdominal pain, or asphyxiation: 
 o ICD-9-CM 518.81, 518.84, 787.0*, 782.2, 789.0*, 786.02, 786.05, 786.1 o ICD-10-CM J96.0*, J96.2*, J96.9*, R06.0*, R06.1, R10.*, R11.*, R22.0*, R22.1, R19.0 	
UpToDate states severe attacks are treated in ED.²³
 
Tachdjian 2020¹
 
Zilberberg 2010²⁴
 
Longhurst & Bork, 2019

Non- severe attack	
Each dose of an on-demand therapy over two acute attack doses is considered an attack. The number of doses dispensed will be calculated from the quantity dispensed and recommended dose and
 
Any on-demand therapy administered outside an inpatient or emergency room setting will be considered a non-severe attack.
	
Utilization	Algorithm and code lists	Source

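### The non-severe attack rule counts a professionally given Ruconest (or on-demand Cinryze) dose before a procedure as an attack, and no planned analysis tests this

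*Protocol*

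**What the plan says.** Non-severe attacks are identified by two routes.

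- **Professional administration.** Protocol section 5.2.1.4: "An attack treated by a healthcare professional will be defined as a medical service claim for an on-demand therapy occurring outside an inpatient or ED". Annex 2 (attack severity) puts it more broadly: "Any on-demand therapy administered outside an inpatient or emergency room setting will be considered a non-severe attack".
- **Dispensed product for self-administration.** Annex 2: "Each dose of an on-demand therapy over two acute attack doses is considered an attack".

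Annex 1 lists off-label short-term prophylaxis before a procedure for two products that can also be given for an acute attack. The Ruconest entry is "50 IU/kg or 1,000 units immediately prior to procedure"; the Cinryze entry is "20 units/kg or 1,000 units immediately prior to procedure". Ruconest is one of the four on-demand drugs in Table 2 (Annex 3). Cinryze is not in that list, but section 5.1.1.2 says it is also used off-label for acute attacks.

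Section 5.4.1.1 divides total attacks by person-months over the six-month baseline. Annex 2 takes home and office costs from medical claims with an on-demand administration at that place of service. The sensitivity analyses in section 5.4.1.4 vary only the five-day window and the two doses assumed to be on hand.

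**The concern.** The attack rule treats an on-demand administration as proof of an attack. The protocol's own drug table names a use of the same product in which no attack has occurred, and the rule has no diagnosis or procedure check to tell the two apart.

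In the attack rate the error can only run upward, because a preventive dose may be counted as an attack and nothing offsets it. The baseline rate feeds the cost-effectiveness model, and section 4 warns that small changes in attack frequency could alter the model's results substantially. The same claims also enter the home and office costs per attack, the split by place of treatment and the on-demand drug shares. For cost per attack the direction cannot be told from the protocol, since a pre-procedure visit may cost more or less than an attack visit.

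**Working it through.** The protocol states no frequency of pre-procedure dosing and no cohort size, so there is no planned figure to reproduce. The check applies the protocol's own estimator.

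**Inputs**
- Baseline length: 6 months (section 5.4.1.1).
- Prior base-case attack rate: 3.39 per month (Annex 3, Table 2).
- Lower comparison rate: one attack every 4 weeks, the coverage requirement for Takhzyro in Annex 4. Per month: (365.25/12)/28 = 1.087.
- s, the share of patients with one professionally given pre-procedure dose in baseline that falls in no other attack episode: **assumed**, 5% to 30%.

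**Effect on one affected patient**

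1 dose / 6 months = 0.167 attacks per month. Relative to 3.39: 0.167/3.39 = 4.9%. Relative to 1.087: 0.167/1.087 = 15.3%.

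**Effect on the cohort rate**

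Added rate = s × 1/6.

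| s (assumed) | Added attacks/month | % of 3.39 | % of 1.087 |
|---|---|---|---|
| 5% | 0.008 | 0.25 | 0.8 |
| 10% | 0.017 | 0.49 | 1.5 |
| 20% | 0.033 | 0.98 | 3.1 |
| 30% | 0.050 | 1.5 | 4.6 |

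**A second way to place s.** Suppose every patient has 0.5 to 1 pre-treated procedure per year (assumption), and Ruconest is used for a quarter of them, borrowing the 25% model share in Table 2 as an illustration. Then s = 0.5 × 0.5 × 0.25 = 6.25% to 1 × 0.5 × 0.25 = 12.5%. The added rate is 0.010 to 0.021 per month, or 0.3-0.6% of 3.39, in the lower part of the range above.

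**Where the error concentrates.** It falls on professionally treated attacks. Table 2's prior outpatient share is 21.3% of non-severe attacks. If all 3.39 attacks were non-severe (a simplification), that stratum would hold 0.213 × 3.39 = 0.72 per month, and 0.008-0.050 would be about 1-7% of it.

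**The case against.** Several points limit the concern, and they stand:

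- Only Ruconest, of the four on-demand drugs in Table 2, has a pre-procedure entry in Annex 1, and the entry is marked off-label. Berinert, Kalbitor and Firazyr have none.
- Section 5.2.1.4 merges professional administrations within five days of each other, or of an emergency visit or admission, into one episode. A dose close to such an event adds no separate non-severe attack.
- For dispensed product, the two-dose allowance can absorb a single pre-procedure dose if the patient has no more than two doses in all. It does not apply to a professionally administered claim.
- Section 5.4.1.5 concedes that no claims algorithm for attacks has been validated. That is a general caveat; it does not identify or size this error.

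A reader might also infer a second defect: that one fill of an older oral drug removes a patient from the cohort. Section 5.1.1.2 says "Patients receiving other prophylactic treatments (see Annex 1) during the baseline period will also be excluded"; danazol has a short course around procedures in Annex 1 ("Administer 5 days before and 2-3 days after procedure"); and the older oral drugs are absent from the footnote "Drugs Indicated Only for HAE: Cinryze, Haegarda, Berinert, Takhzyro, Ruconest, Kalbitor, Firazyr, Orladeyo". The documents do not support that reading. No any-fill rule is stated, and a fill for another condition is not plainly receipt of prophylaxis. The 90-day tests for Cinryze and Ruconest separate acute from prophylactic use, a distinction the older oral drugs do not need because Annex 1 gives them no acute dose. Among those drugs only danazol has a pre-procedure entry. A fill or days threshold may sit in an analysis plan that is not shown, and no number of lost patients can be derived.

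**Conclusion.** The point holds for professionally administered Ruconest, and for Cinryze where it is handled as on-demand: as written, the rule counts a pre-procedure dose without an attack as a non-severe attack, and no planned sensitivity analysis would show it.

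The size is modest. Under the assumed 5-30% of patients affected, the cohort rate is overstated by 0.008-0.050 attacks per month, at most 1.5% of the base case and 4.6% of a one-per-four-weeks rate. It would be a mistake to infer that the baseline rate is materially wrong; the protocol gives nothing from which the true frequency could be worked out. This is a low-cost improvement to a definition, not a flaw that invalidates the primary objective.

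**What to change.** In Annex 2, flag any professionally administered Ruconest claim (and any Cinryze claim counted as on-demand) dated on the day of, or the day before, a surgical, dental or endoscopic procedure claim. In section 5.4.1.4, add a sensitivity analysis giving the non-severe rate, the total attack rate and the cost per attack with and without the flagged claims, together with the number flagged.

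The flag should not depend on a diagnosis code. The codes 277.6 and D84.1 are described in Annex 2 as often associated with HAE; they do not mark an attack and could sit on a pre-procedure claim.

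**Cost.** One sentence in Annex 2, one added bullet in section 5.4.1.4, a procedure code list and one rerun on claims already held. A true attack treated next to a procedure is dropped from the sensitivity version, which is why both figures should be reported. Section 5.3.1.1 describes medical and pharmacy claims only, so a dental procedure can be flagged only if it appears among them.

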5.2.1.8 Hospitalization utilization

For those patients with severe attacks, defined by inpatient hospitalization or ED visit, we will calculate the percentage of patients hospitalized. Of those hospitalized, we will also estimate utilization for the following:

- Percent of patients receiving cricothyrotomy/tracheotomy
 - Percent that also receive artificial respiration
- Percent of patients intubated
 - Percent that also receive artificial respiration

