cricothyrotomy/ tracheotomy	emergency tracheotomy (31603) and an emergency cricothyrotomy (31605)	
Dillon 2013²⁵
 
Esposito²⁶

intubation	The appearance of any of the following encounters CPT - 31500 ICD10 - 09HN7BZ, 0DH57BZ, 0DH58BZ, 0WHQ73Z, 0WHQ7YZ, 09HN8BZ, 0B21XEZ, 0BH13EZ, 0BH17EZ, 0BH18EZ, 0CHY7BZ, 0CHY8BZ ICD9 - 96.04, 96.7x, 96, 96.0,96.5	Pandya 2019²⁷ Singh 2020²⁸ De novo code look up
artificial respiration	The appearance of any of the following encounters Invasive mechanical ventilation: CPT - 94002, 94003, 94004, 94005, E0472, K0534 ICD10 - 5A1935Z, 5A1945Z, 5A1955Z noninvasive ventilation: CPT - 94660, A7027, A7034, A7044, E0452, E0470, E0471, E0601, K0183, K0193, K0194, K0532, K0533 ICD10 - 5A09459, 5A09557, 5A09357, 5A09358, 5A09359, 5A0935B, 5A09457, 5A09458, 5A0945B, 5A09558, 5A09559, 5A0955B ICD9 - 93.90 ventilation NOS: CPT- 94656, 94657 ICD10 - 5A0920Z, 5A0945Z, 5A0955Z, 5A19054, 5A0935Z, 5A09358, 5A0935B,	Pandya 2019²⁷ Singh 2020²⁸ Rosenthal 2020²⁹ De novo code look up
Costs	Algorithm and code lists	Source
Home nurse treatment	Standard cost amount for medical service claims with an on-demand drug administration where the place of service is ‘home’	
Physician office visit	Standard cost amount for medical service claims with an on-demand drug administration where the place of service is ‘office’	
ED visit	Standard cost amount for medical service claims where the type of service is coded as ‘emergency room, professional or facility’	
Hospitalization	Standard cost amount for medical service claims where the type of service is coded as ‘acute inpatient facility’	

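### The Annex 2 airway code lists are not aligned across code systems and may misclassify tracheotomy, intubation and ventilation, in a direction that differs by outcome

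*Protocol*

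**What the plan says.** Section 4 makes airway procedures in patients hospitalized for severe attacks part of the primary objective. Section 5.2.1.8 sets the base: "Of those hospitalized, we will also estimate utilization for the following", followed by cricothyrotomy/tracheotomy and intubation, each with the share who also receive artificial respiration. Section 5.2 sends the reader to Annex 2 for all definitions, so the lists there are the operative ones.

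- **Cricothyrotomy/tracheotomy:** "emergency tracheotomy (31603) and an emergency cricothyrotomy (31605". No code system is named and no ICD procedure code is given. The sources are a paper on the emergent surgical airway and a surgical billing guide.
- **Intubation:** starts with "CPT - 31500 ICD10 - 09HN7BZ, 0DH57BZ, 0DH58BZ", continues through further ICD-10 codes, and ends with "ICD9 - 96.04, 96.7x, 96, 96.0,96.5".
- **Artificial respiration:** one list with three blocks, any code counting. The invasive block reads "CPT - 94002, 94003, 94004, 94005, E0472, K0534 ICD10 - 5A1935Z, 5A1945Z, 5A1955Z". The non-invasive block has CPT/HCPCS, ICD-10 and one ICD-9 code, 93.90. The unspecified block reads "CPT- 94656, 94657 ICD10 - 5A0920Z, 5A0945Z, 5A0955Z, 5A19054, 5A0935Z, 5A09358, 5A0935B".

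The intubation and artificial respiration rows both cite a de novo code look-up as a source. The tracheotomy row does not.

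Table 2 in Annex 3 sets the four resulting percentages beside the earlier base-case values: tracheotomy among hospitalized 40.0%, ventilation among tracheotomy patients 40.0%, intubation among hospitalized 60.0%, and ventilation among intubated 26.7%.

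**The concern.** The procedures are measured in the same patients, whose cohort entry runs from October 2008 to October 2019 (Section 5.1.1.2), yet they are searched with different reach. A procedure recorded only in a code system that its row omits is counted as not done. An entry filed in the wrong row moves a patient from one outcome to another.

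Section 3 says the results, with supplemented literature, will supply updated inputs to the cost-effectiveness model. If the tracheotomy percentage came out well below 40.0%, a reader could not tell a real-world difference from the effect of a two-code search. Neither the sensitivity analyses in Section 5.4.1.4 nor the limitations in Section 5.4.1.5 cover the procedure code lists.

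**Working it through.** The protocol states no figure for code capture, so there is none to reproduce. The check is a count of codes, followed by illustrations under stated assumptions.

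**Step 1. Entries by code system, Annex 2**

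| Outcome or block | CPT/HCPCS | ICD-10 | ICD-9 |
|---|---|---|---|
| Cricothyrotomy/tracheotomy | 2 (system not named) | 0 | 0 |
| Intubation | 1 | 12 | 5 |
| Ventilation, invasive | 6 | 3 | 0 |
| Ventilation, non-invasive | 13 | 12 | 1 |
| Ventilation, unspecified | 2 | 7 | 0 (as the text reads) |

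The five ICD-9 entries under intubation are 96.04, 96.7x, 96, 96.0 and 96.5. Artificial respiration as a whole has 6 + 13 + 2 = 21 CPT/HCPCS codes and one ICD-9 code.

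**Step 2. Tracheotomy among hospitalized patients.** If the two codes find a share c of true cases, measured % = c × true %. Taking the base-case 40.0% as the truth, for illustration only:

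- c = 100%: 40.0%
- c = 90%: 36.0%
- c = 70%: 28.0%
- c = 50%: 20.0%

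The protocol gives no value for c.

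**Step 3. Ventilation among intubated patients.** Let f be the share of stays coded in ICD-9 and c9 the capture of ventilation in those stays, with full capture elsewhere. Then measured % = true % × (f × c9 + 1 − f).

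The protocol gives neither f nor a date for the change to ICD-10. Assume a change on 1 October 2015 and entries spread evenly. The entry window, 10 October 2008 to 3 October 2019, is 4011 days, of which 2547 fall before that date: f = 2547/4011 = 63.5%. Moving the date one year either way gives 54.4% to 72.6%. This is a share of calendar time, not of patients. Takhzyro was approved only in August 2018, so entries may cluster late and f may be smaller.

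With f = 63.5% and a true 26.7%:

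- c9 = 100%: 26.7%
- c9 = 90%: 26.7 × 0.9365 = 25.0%
- c9 = 70%: 26.7 × 0.8095 = 21.6%
- c9 = 50%: 26.7 × 0.6825 = 18.2%

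**Step 4. Intubation.** This row has all three code systems, so no system is missing. The visible risk runs the other way. If 96.7x denotes ventilation (the protocol does not define it), or if the stems 96 and 96.0 take in other procedures, patients who were not intubated are counted as intubated. They also enter the denominator of Step 3, and lower that percentage if the artificial respiration list does not find them.

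**Step 5. Ventilation among tracheotomy patients.** Missed tracheotomies leave both numerator and denominator. Suppose 40% of true tracheotomy patients are ventilated, half of the tracheotomies are found and ventilation itself is fully captured. The found half could hold all of the ventilated patients (40/50 = 80%) or none (0/50 = 0%). No direction follows.

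**The case against.** A reader might infer that the four model inputs are under-captured. The documents do not support that.

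- Section 5.3.1.1 says the data derive from claims for all medical and pharmacy services, so CPT-coded claims for hospitalized patients may be visible. If they capture every case, the loss is zero.
- Intubation is, if anything, over-captured, and ventilation among tracheotomy patients has no clear direction.
- ICD-9 ventilation codes may be misfiled rather than absent. Artificial respiration also counts any of 21 CPT/HCPCS codes, which do not depend on the ICD version, so a block without an ICD-9 line does not by itself lose the outcome.

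A reader might also take the sentence in Section 5.2.1.4, "Symptoms and diagnoses codes were cross referenced in a de novo code search to capture both ICD-9 and ICD-10 codes", as a promise that the procedure lists break. It concerns symptoms and diagnoses used to define attacks and commits to nothing about procedures.

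Three further points are fair. Restricting tracheotomy to emergency procedures is a sourced choice and coherent for acute attacks, although Sections 4 and 5.2.1.8 state no such limit. The unspecified ventilation list ends on a comma, so text may be lost there and its missing ICD-9 line is less certain. Table 2 sets new results beside prior values without saying that they replace them automatically.

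All of this limits what can be said about size and direction. It does not explain why one of three procedures measured in the same stays is searched without any ICD procedure code, or why 96.7x and the broad stems sit under intubation.

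**Conclusion.** The point holds as a risk of misclassification from unaligned code lists, not as demonstrated under-capture.

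- Tracheotomy among hospitalized patients may be under-counted relative to intubation.
- Intubation may be over-counted.
- Ventilation among intubated patients may be under-counted in stays coded in ICD-9.
- The direction for ventilation among tracheotomy patients is unclear.

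The size cannot be computed from the protocol and may be zero. The illustrated falls, from 40.0% to between 36.0% and 20.0% and from 26.7% to between 25.0% and 18.2%, rest on assumed capture of 90% down to 50%. The second set also rests on an assumed coding-change date and even entry over time. The lists are fixed in Annex 2 and feed primary-objective percentages, so they should be aligned before use.

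**What to change.** Before the query is run:

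1. Add ICD-9 and ICD-10 procedure codes to the cricothyrotomy/tracheotomy row, using the same de novo look-up as the other two rows, and count them only within attack hospitalizations. Label 31603 and 31605 with their code system. Report the emergency-only result from those two codes alongside the extended one, so that the effect of the extension can be seen.
2. Add ICD-9 procedure codes for invasive and unspecified ventilation.
3. Check 96.7x and the stems 96 and 96.0 against the code set, and move or remove any entry that does not denote intubation.

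The cost is a code-list edit and one extra reported line. The downside is that the ICD extension may bring in some non-emergency tracheotomies; the restriction to attack hospitalizations and the side-by-side result limit that.
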